We will power the study to detect a 250mL difference in calculated intra-operative blood loss between groups. This effect size has been used in the total hip literature, and it is considered to be a clinically significant difference in blood loss¹⁵. Our analysis shows that 12 patients are required in each arm of the study (24 patients total) to achieve 81% power with an independent-sample t-test and statistical significance set to alpha equal to 0.05. Expecting that 10-25% of patients will be excluded, we will aim to enroll a total of 30 patients in this study.

Patients aged 18 or younger will be screened for study eligibility

3. Interventions or Observations – what data are going to be collected and from what source?

Only anesthesiologists agreeing to participate in the study will be paired with the study surgeons. Anesthesia will be conducted in a standardized fashion. The anesthesiologist will perform a neuraxial block (epidural, spinal, combined-spinal epidural) as well as administer general anesthesia. A neuraxial block will be placed using bupivicaine. A balanced general anesthetic utilizing a combination of either isoflurane, sevoflurane with or without nitrous oxide, vecuronium, midazalam and either fentanyl, morphine or dilaudid as the narcotic will be used at the discretion of the anesthesiologist. If a combined-spinal epidural is unsuccessful and an epidural and/or spinal are successfully obtained, the patient will still be included in the study. Patients not receiving neuraxial anesthesia will be excluded from the study. Arterial and venous access will be obtained in the usual sterile manner for monitoring.

The blood pressure target will be 20-25% below baseline, which will be achieved primarily with the combination of the general anesthesia and the neuraxial anesthesia. For blood pressure above this range, the epidural will be dosed with a short-acting local anesthetic, and/or the depth of the general anesthetic and will be titrated as per the anesthesiologist's judgment. For hypotension below this range, intravenous pressors, crystalloid, colloid or blood will be given. The technique of induced hypotension will not be utilized during these cases. Additional maintenance IV fluids or colloid will be given to maintain urine output of at least 0.5-1ml/kg/hr. Toradol and IV acetaminophen may be given towards the end of the case per the anesthesiologist's discretion.

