Bilateral VRO will be performed as per the surgeon's routine practice. In general, the operative extremity will be prepped and draped in the usual sterile fashion. Prior to incision, the anesthesiologist will administer a loading dose of 100 mg/kg of EACA with a max of 4-5 grams up to 1 hour prior to incision. During the case, an infusion of 33 mg/kg/hr (max of 1 gram/hr) will be maintained. The use of EACA will be terminated at the end of the case. Patients randomized to the placebo arm will be

infused with a comparable volume of normal saline prepared by the pharmacy. All participating anesthesiologists will not be blinded in this study. A direct lateral approach to the femur will be used, and standard surgical techniques for intra-operative hemostasis will be utilized. The surgeon will perform bilateral femoral osteotomies and associated soft tissue surgery and pelvic osteotomy. After all hardware is placed, the wound will be thoroughly irrigated and suctioned. A deep drain will be placed on each operative side, and the wound will be closed in layers. Intra-operatively, a cell saver will be used, and the volume (mL) of auto-transfusion will be recorded.

Hematocrit levels will be monitored regularly in the post-operative period. As per protocol, a post-op hematocrit will be drawn in the PACU, and subsequently, daily labs will be obtained unless specified by the medicine or surgical attending. Routine, daily inpatient CBC data and drain output will be reviewed. Inpatient and office records will be accessed to help identify postoperative complications. The criteria for transfusion of blood products will be a hemoglobin level of < 7.0 g/dL or a hemoglobin level of < 10.0 g/dL with clinical signs of symptomatic anemia (e.g., unexplained tachycardia, hypotension unresponsive to fluids or vasopressors, change in mental status, low urine output, and shortness of breath). Blood will be administered 1 unit at a time, and the presence of symptoms or signs will be reassessed after each unit. This algorithm may be altered by the treating physician (e.g., PACU attending, surgeon, pediatrician, or the OR anesthesiologist), however all decisions will be supported by reasonable documentation. Drains will be removed on POD 2 unless specified by the attending surgeon, and the 24-hour clock will begin once the patient is in the PACU. All drains, patient charts, and patient rooms will be clearly labeled in order to identify study patients.

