All tests and imaging used in this study are considered standard of care.

Randomization Process:

The patients will be randomized into one of 2 groups: (1) Loading dose and infusion of EACA (2) Equivalent volume of normal saline prepared by the pharmacy. An EACA loading dose of 100 mg/kg with a max of 4-5 grams will be given up to 1 hour prior to incision. During the case, an EACA infusion of 33 mg/kg/hr (max of 1 gram/hr) will be maintained. The use of EACA will be terminated at the end of the case. Assignment of patients will be made based on a sequential treatment assignment or minimization strategy in order to ensure an even distribution of patients in each treatment arm. More specifically, each patient will be randomized to the treatment arm that would minimize differences between groups. Randomization will be stratified by sex and surgery type (bilateral VRO, bilateral VRO with associated soft tissue or osseous procedure) so that the number of male/female patients and VRO/associated procedure patients will be balanced in each study group between trial arms.

The Biostatistics Core of the HSS Healthcare Research Institute will randomize each patient based on the minimization strategy. It will be a double-blind experiment with all parties, except the pharmacy, anesthesiologist, and designated research assistant, being blinded to the randomization schedule (surgeon, medical staff, and patient). Patient recruitment will continue until a total of 30 patients are enrolled.

Treatment Groups:

Bilateral VROs will be performed as per the study surgeon's routine practice. In general, the operative extremity will be prepped and draped in the usual sterile fashion. Prior to incision, the anesthesiologist, will administer a loading dose of 100 mg/kg of EACA with (max of 4-5 grams) or an equivalent volume of normal saline prepared by the pharmacy. The loading dose may be give up to 1 hour prior to incision. During the case, an EACA infusion of 33 mg/kg/hr (max of 1 gram/hr) will be maintained. Only anesthesiologists agreeing to participate in the study will be paired with the study surgeons, and all anesthesiologists will be aware of a patient's randomization to the treatment or placebo group.

Outcome Measures

Primary outcome: Calculated total blood loss.

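### Anesthesiologists are told the arm without a stated reason, although they manage fluids and intra-operative blood and the primary outcome is computed from hematocrit and units transfused

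*Combined protocol and SAP*

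**What the plan says.** The unblinding is deliberate and stated twice. Section 3 (Interventions or Observations) says "All participating anesthesiologists will not be blinded in this study", and the Treatment Groups text repeats that "all anesthesiologists will be aware of a patient's randomization to the treatment or placebo group". Neither place gives a reason.

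The Randomization Process text says: "It will be a double-blind experiment with all parties, except the pharmacy, anesthesiologist, and designated research assistant, being blinded to the randomization schedule". The same sentence names the surgeon, the medical staff and the patient as blinded. The control arm is described there as "Equivalent volume of normal saline prepared by the pharmacy".

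On intra-operative management, Section 3 sets a blood-pressure target and then says: "For hypotension below this range, intravenous pressors, crystalloid, colloid or blood will be given". Further fluid or colloid is titrated to a urine-output target. Transfusion has hemoglobin thresholds, one-unit steps and reassessment after each unit, but "This algorithm may be altered by the treating physician". The operating-room anesthesiologist is one of the physicians listed there, and departures must be documented.

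The primary outcome, calculated total blood loss, is computed under Outcome Measures and again under Data Analysis from the fall in hematocrit and the number of units transfused.

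**The concern.** A placebo protects a trial only if the people who can influence the outcome do not know who receives it. Here the plan has a placebo made and then tells the person giving it which arm it is. That person also decides much of what enters the outcome formula. Extra crystalloid or colloid lowers a later hematocrit and so raises calculated blood loss. A unit of blood adds to the transfusion term and also changes the hematocrit.

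If fluid or blood is given more readily in one arm because the arm is known, part of the observed difference reflects management and not the drug. The plan could not detect this. The operating-room data list in Section 3 covers anesthetic, operative time, transfusion, cell saver and complications, but not fluid or pressor volumes. The adjusted model under Data Analysis contains age, sex, BMI and type of anesthesia only.

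**Working it through.** **The plan's own figures.** The plan gives no figure for bias from unblinding. The sample-size section supplies a difference of 250 mL, SD 233.69 mL, 12 per arm, alpha 0.05 and stated power of 81%. Data Analysis specifies two-sided tests. With these inputs a two-sided t-test has 70.7% power; a one-sided test gives 81.4%, so the stated power reproduces only one-sided. That is a separate matter. The check below takes n and SD from this section and uses the two-sided test.

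**Step 1: can the unblinded person reach the outcome?**

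| Term in the outcome | Who can act on it | What limits that person |
|---|---|---|
| Postoperative hematocrit | Anesthesiologist, through choice and volume of intra-operative fluid | Blood-pressure and urine-output targets |
| Units transfused | Anesthesiologist in the operating room, sharing the power to depart from the algorithm with other physicians | Hemoglobin criteria, one-unit steps, documentation |

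Both terms can be reached. The limits narrow discretion but do not remove it: no rule says which of the four options for hypotension to use.

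**Step 2: what one hematocrit point is worth.** The printed term is EBV × (preoperative Hct − postoperative Hct). Assume a boy of 1.2 m and 25 kg; the constants are the plan's own for males.

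- EBV = 0.3669 × 1.2³ + 0.03219 × 25 + 0.6041 = 0.634 + 0.805 + 0.604 = 2.04 L.
- One point of dilution = 0.01 × 2.04 L, or about 20 mL of red-cell volume.

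**Step 3: what a spurious shift does to the test.** Assume no drug effect and that SD 233.69 applies. The plan states that SD for intra-operative loss, so using it for total loss is an assumption.

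- Standard error of the difference at 12 per arm = 233.69 × √(2/12) = 95.4 mL.
- Noncentrality = shift / 95.4: 0.52 for 50 mL and 1.05 for 100 mL, on 22 degrees of freedom.

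| Assumed shift | False-positive rate, 12 per arm | False-positive rate, 15 per arm |
|---|---|---|
| 0 mL | 5% | 5% |
| 50 mL | 7.9% | 8.7% |
| 100 mL | 17.1% | 20.5% |

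The shift sizes are assumptions. By dilution alone in the child above, 50 mL would need an average difference of 50 / 20.4 = 2.4 hematocrit points between arms, and 100 mL would need 4.9.

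**The case against.** The strongest reply is that the choice is disclosed and hedged. The sentence that calls the trial double-blind also lists who is and is not blinded. Targets and transfusion criteria are set, and departures must be documented. The surgeon and medical staff are blinded, and the surgeon, PACU attending and pediatrician share the power to alter the algorithm. The hemoglobin used may be the lowest of the stay, which may weaken the effect of intra-operative fluid. All of this stands and limits the bias. It does not explain why the anesthesiologist must know the arm.

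Four stronger readings are tempting, and the documents do not support them.

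- **One extra unit equals the whole 250 mL target, so two such patients of 12 shift the arm mean by at least 42 mL (2 × 250 / 12).** The plan's 250 mL is the mean volume of a transfused unit, not the loss it represents. An intra-operative unit also raises the postoperative hematocrit. Leaving out the division in the transfusion term and assuming a unit hematocrit of 0.55 to 0.70, the unit carries 0.1375 to 0.175 L of red cells. The net rise is then 75 to 112.5 mL, and two of 12 patients shift the mean by about 12 to 19 mL. Two of 12 is itself an assumption.
- **The printed transfusion term makes a unit worth 1.25 L, so the same two patients shift the mean by 208 mL.** That assumes hematocrit 0.38 to 0.28 and comes from dividing by a hematocrit difference in an expression with an unbalanced bracket. It is a question about the formula and would remain under perfect blinding.
- **One hematocrit point is worth 62 mL.** That divides by a mean hematocrit of 0.33, which the printed red-cell term does not do.
- **The transfusion secondary outcome is biased throughout.** It is headed as postoperative requirement, where blinded staff share the decisions. The clearer exposure is intra-operative transfusion, which the plan also documents for analysis. The formula does not say whether intra-operative units count.

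Feasibility is also not fully shown: the documents do not say who prepares the EACA or whether the containers can be made to look alike.

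**Conclusion.** The concern holds as a possible bias of unknown direction and size, arising from a disclosed but unexplained choice. An unblinded anesthesiologist keeps discretion, within stated limits, over both terms of the primary outcome, and the plan records too little to check whether the arms were managed alike. The documents do not show that bias will occur or that it would favor EACA. The illustrations rest on an assumed child, assumed shift sizes and the plan's SD; they show how sensitive a trial of this size is, not what to expect. The disclosed exceptions mean that a careful reader is not deceived about who is blinded, but the double-blind label claims more than the design delivers. This is an inexpensive improvement that should be made; it does not by itself invalidate the trial.

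**What to change.** Have the pharmacy dispense load and infusion for both arms in coded, matched containers with matched volumes and rates. Blind the anesthesiologist, and keep an emergency code break in the pharmacy. Sample size, alpha and power are unchanged. The cost is labelling work, a code-break procedure and one extra step in an emergency. It assumes that the pharmacy can also prepare the EACA, which the sponsor should confirm.

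If the anesthesiologist must remain unblinded:

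- state the reason in the protocol;
- replace the double-blind label with the list of blinded parties already given under Randomization Process;
- add intra-operative fluid, colloid and pressor volumes to the operating-room data list in Section 3;
- compare those volumes and the intra-operative transfusion decisions by arm in a prespecified sensitivity analysis. Units and supporting documentation are already called for, so only the volumes and the analysis are new.

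This alternative costs a few data fields and one analysis. It makes differences in management visible but does not prevent them.

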The Effect of Intravenous EACA on Blood Loss and Transfusion Requirements After Bilateral VRO

Protocol and Analysis Plan

NCT # NCT02257580

Approved 12/10/2014

1. What is the Study Design

Experimental:

Randomized controlled clinical trial (RCT)

2. Who will be recruited and enrolled?

Inclusion Criteria:

Patients will be recruited from the practices of [name] and [name]. Inclusion criteria will include the following:

- Age less than or equal to 18
- Scheduled for elective bilateral VRO with or without associated soft tissue and osseous procedures

Exclusion Criteria:

All patients will be asked to discontinue acetylsalicylic acid (ASA), antiplatelet agents, and hormone replacement and hormonal contraceptive agents at least 7 days prior to surgery. Other than ASA, these agents will be held 6 weeks postoperatively.

- Preoperative use of an anticoagulant (Plavix, warfarin, lovenox, etc.)
- History of hypersensitivity to EACA
- History of thromboembolic event (e.g., PE or DVT)
- History of renal insufficiency or failure
- Congenital or acquired coagulopathy as evidence by INR >1.4 or PTT > 1.4 times normal, or Platelets <150,000/mm³ on preoperative laboratory testing
- Use of hormone replacement therapy or hormonal contraceptive agent within 7 days prior to surgery
- Pregnant
- Breastfeeding
- Older than 18 years of age
- Patients not receiving neuraxial anesthesia

This trial will be registered on ClinicalTrials.gov. All patients undergoing bilateral VRO by the study surgeons ([name]) will be identified in their office and screened for eligibility as potential patients for participation in the study. A research assistant will review the office and operative calendars of the study surgeons each week to identify and recruit potential patients. The assistant will record on the CONSORT diagram any reasons for ineligibility/exclusion.

The surgeon, a co-investigator or research assistant will obtain consent prior to surgery, at the patient's preadmission screening visit. All authors on the protocol, in addition to their research assistants, will be designated to obtain consent.

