Attending surgeons, orthopedic surgery residents, physician assistants and research assistants involved with this study will assist in data collection. For each patient, we will collect demographic data, pre-operative CBC data, intra-operative cell saver auto-transfusion volumes, post-operative number of packed red blood cell units transfused, post-operative CBC data, post-operative drain outputs, and post-operative complications. This information will be gathered from the peri-operative medical records and electronic medical records.

A sticker will be place on the front of each participating patient's chart identifying him or her as a study patient. Their enrollment will also be communicated in the clinician rounding notes for each patient. Drains will be labeled for each study participant as well, and nurses will record the drain outputs per their floor protocol.

Data recorded from the electronic medical record will include:

- Date of surgery
- Patient age at the time of surgery
- Patient sex
- Patient height (cm) and weight (kg) at time of admission
- Preoperative CBC data and coagulation study data

- Postoperative hemoglobin on all inpatient days postoperatively (g/dL)
- Transfusion requirement during inpatient stay (units required)
- Transfusion reaction
- Total 24-hour drain output
- Postoperative day and time of discharge
- Chart review of progress notes for evidence of clinically significant VTE
- Chart review of progress notes for evidence of reoperation, hematoma, seroma, or postoperative infection

Data recorded from the operating room record will include:

- Anesthetic used (e.g., spinal/epidural, general, etc.)
- Operative times (minutes)
- Intra-operative transfusion requirements (units of blood)
- Use of cell saver intraoperatively (auto-transfusion volume, mL)
- Intra-operative complications

Data recorded from outpatient postoperative office records will include:

- Chart review of progress notes for evidence of clinically significant VTE through six weeks post-operatively
- Chart review of progress notes for evidence of re-operation, hematoma, seroma, or postoperative infection through six weeks post-operatively

Patients will be randomized to either the intervention or control group, as per randomization protocol described elsewhere in the proposal. For patients who are randomized to the control group, study data will be collected in the same manner as for the intervention group.

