Secondary outcomes of interest: Postoperative transfusion requirements (allogeneic blood transfusion and intraoperative cell saver utilization), post-operative blood loss, length of stay, and post-operative complications.

Calculated total blood loss will be determined from the difference between the preoperative hemoglobin and the postoperative hemoglobin (or the lowest postoperative hemoglobin during the hospital stay prior to transfusion). Based on hemoglobin balance, the estimated blood loss will be calculated according to the formula by Nadler et al.¹⁷:

```
Estimated Blood Volume (EBV) = (k_1 \text{ x Height}^3 \text{ (m)}) + (k_2 \text{ x Weight (kg)}) + k_3
For men, k_1 = 0.3669, k_2 = 0.03219, and k_3 = 0.6041
For women, k_1 = 0.3561, k_2 = 0.03308, and k_3 = 0.1833
```

Multiplying the EBV by the hematocrit (Hct) gives the red blood cell (RBC) volume. As such, a change in the RBC volume can be calculated from a change in the Hct level^{23,24}:

```
Total RBC volume loss = EBV x (Hct Preop – Hct Postop)
```

Transfusions (mean volume per unit at HSS, 250 mL) can be taken into account by calculating the total blood loss¹⁶:

Total blood loss (L) = Total RBC volume loss + (No. of Units Transfused x 0.25) / (Hct Preop – Hct Postop) / 2)

The rate of perioperative blood transfusions, both intraoperative and postoperative, will be documented for analysis.

The criteria for transfusion of blood products will be a hemoglobin level of < 7.0 g/dL or a hemoglobin level of < 10.0 g/dL with clinical signs of symptomatic anemia (e.g., unexplained tachycardia, hypotension unresponsive to fluids or vasopressors, change in mental status, low

urine ouput, and shortness of breath). Blood will be administered 1 unit at a time, and the presence of symptoms or signs will be reassessed after each unit. This algorithm may be altered by the treating physician (e.g., PACU attending, surgeon, or the OR anesthesiologist), however all decisions will be supported by reasonable documentation. Drains will be removed on POD 2 unless specified by the attending surgeon. Of note, the chart of the patient will clearly indicate him/her as a study patient.

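### Allogeneic blood is recorded only in units, and each unit enters the primary outcome at a fixed 250 mL; the volume each child actually received should be recorded and used

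*Combined protocol and SAP*

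**What the plan says.** Three entries in section 3 define how allogeneic blood is captured. The data-collection paragraph lists "post-operative number of packed red blood cell units transfused". The electronic-record list has "Transfusion requirement during inpatient stay (units required". The operating-room list has "Intra-operative transfusion requirements (units of blood". None asks for a volume. Cell-saver return, by contrast, is recorded in mL in the same operating-room list.

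The Outcome Measures part of section 3 and the Data Analysis part of section D both state: "Transfusions (mean volume per unit at HSS, 250 mL) can be taken into account by calculating the total blood loss". The transfusion term is printed as "No. of Units Transfused x 0.25) / (Hct Preop – Hct Postop) / 2", so each unit contributes 0.25 L before division by a hematocrit term.

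On administration, section 3 says "Blood will be administered 1 unit at a time", and then "This algorithm may be altered by the treating physician", provided the decision is documented. On population, section 2 requires "Age less than or equal to 18" and sets no minimum age or weight.

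Section D also treats the postoperative transfusion requirement as a continuous secondary outcome, compared between arms in the same way as the primary. Weight in kg is collected, but it does not scale this outcome, is not a minimization factor and is not a regression covariate (BMI is).

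**The concern.** A unit count stands in for a volume, at one fixed conversion, in patients who may range from small children to adolescents. The conversion is wrong for a particular child in two situations: a part-unit is entered as a full unit, or the unit's volume was not 250 mL. The plan has no scoring rule for a part-unit, so two abstractors could enter the same event differently. The formula then divides the volume by a hematocrit term, so an error in mL of product becomes a larger error in mL of calculated loss.

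At stake are the precision of the primary comparison in a trial of 12 evaluable patients per arm and, under conditions set out below, its direction. The secondary transfusion outcome is also affected: one unit is a very different amount relative to body size in a small child and in an adolescent.

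**Working it through.** **Inputs from the plan.** 250 mL per unit; target difference 250 mL; SD 233.69 mL; 12 per arm; stated power 81%; two-sided alpha 0.05.

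**Assumptions (not in the plan).** Body weights of 12 and 60 kg; a child given 150 mL and scored as one unit; mean hematocrit 0.31 (0.25 to 0.35 as a range); red-cell content of the product 60%; all transfusion rates.

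**The plan's own figure.** The stated 81% is reproduced by a one-sided t-test at 0.05 (81.4% with 12 per arm). The two-sided test that section D specifies gives 70.7%. That mismatch is a separate matter; here the 250 mL and 233.69 mL serve only as yardsticks.

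**Error for one child.**
- Product error: 250 − 150 = 100 mL.
- Divided by mean hematocrit: 100 / 0.31 = 323 mL.
- Counting only red cells: 0.6 × 100 / 0.31 = 194 mL.
- A half-unit miscount: 125 / 0.35 = 357 mL to 125 / 0.25 = 500 mL.
- A one-tenth-unit discrepancy: 25 / 0.35 = 71 mL to 25 / 0.25 = 100 mL.

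These figures divide by a mean hematocrit, which is not what is printed. The printed divisor is a hematocrit difference with unbalanced brackets. For the half-unit case, with assumed hematocrit drops of 0.05 to 0.15, it gives anything from 417 to 5000 mL depending on how the brackets are read.

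**Effect on an arm mean, per misscored child.** 323 / 12 = 27 mL; 194 / 12 = 16 mL. Against the 250 mL target, that is about 11% and 6%.

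**Noise, as an illustration.** Suppose every transfused child is over-counted by an amount uniform between 0 and 0.5 unit, at mean hematocrit 0.30. The error then runs from 0 to 125 / 0.30 = 417 mL. With a proportion q transfused, the variance is q × 417²/3 − (q × 208)². The total SD is the square root of 233.69² plus that variance.

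| q | total SD (mL) | two-sided power, 12 per arm |
|---|---|---|
| no error | 233.69 | 70.7% |
| 10% | 245 | 66.7% |
| 25% | 258 | 62.3% |
| 50% | 270 | 58.4% |

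**Bias, as an illustration.** With the same scoring in both arms, bias = (difference in transfusion rates) × (mean error per transfused child). For a half-unit over-count in every transfused child at hematocrit 0.30:
- 30% v 20%: 0.10 × 417 = 42 mL.
- 60% v 20%: 0.40 × 417 = 167 mL.
- Equal rates: 0 mL.

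**Body size.** 250 / 12 = 20.8 mL/kg; 250 / 60 = 4.2 mL/kg. The same score of one unit covers about a fivefold range.

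**The case against.** The strongest defence is that the error is hypothetical. The stated algorithm gives one unit and then reassesses. The sentence allowing departures does not mention part-units, and it requires documentation. Neither the transfusion rate nor the frequency of part-units is given. All of this stands, and it is why the trial-level figures above are illustrations.

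Four stronger readings are tempting, and the documents do not support them.

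- A reader might infer that only whole units can be entered. The plan never says so. If fractions were entered, the part-unit error would largely disappear. What remains is that the plan is silent and that 250 mL is a mean even for full units.
- A reader might set the 320 mL beside the 250 mL target and conclude that one child can overturn the result. The first is one patient's error and the second is a difference between group means; the arm-level shift is 16 to 27 mL. Small discrepancies also give small errors.
- A reader might infer that the primary comparison is biased. That needs both misscoring and unequal transfusion rates, and neither is established. The noise figures may also overstate the loss: if the 24 historical cases were calculated in the same way, which the plan does not say, part of this noise is already in the SD.
- A reader might infer that ignoring body size invalidates the secondary outcome. Randomization protects that comparison, because both arms use the same unit, so the cost is precision. The plan also already documents how often transfusion occurs, during and after surgery, and collects weight, so an approximate mL/kg at the nominal 250 mL can be derived without new data.

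**Conclusion.** The point holds as a measurement weakness with an inexpensive remedy. A fixed 250 mL per unit is a poorer input to the primary outcome than the volume actually given, in a population with no lower size limit and with no rule for part-units. Under the assumptions stated (150 mL scored as 250 mL, mean hematocrit 0.31, red-cell content 60% or not considered), each affected child shifts a 12-patient arm mean by about 16 to 27 mL. The general effect is added noise; bias is conditional, and the documents do not allow it to be quantified. For the secondary transfusion outcome, the loss is one of precision.

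Much of the magnification comes from the hematocrit divisor. As printed, that divisor is a separate defect, and recording the volume does not cure it.

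**What to change.** - **Section 3, data lists:** add the actual volume in mL of red cells transfused, intra-operatively and postoperatively, alongside the number of units.
- **Section 3, Outcome Measures, and section D, Data Analysis:** in the blood-loss formula, replace units × 0.25 with the recorded volume in litres.
- **Section D, secondary outcomes:** report the transfusion outcome in mL/kg, using the weight already collected, next to the transfusion rate already planned. Keep unit counts as description.

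The cost is one field, slightly more abstraction time from records already being reviewed, and a few words in the analysis section. The divisor needs its own correction. Nothing here changes when or how patients are transfused.

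### Minimization is described without a random element, and the unblinded research assistant is not kept out of recruitment, so allocation is predictable to anyone holding the full tally

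*Combined protocol and SAP*

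**What the plan says.** The Randomization Process text in section 3 introduces the method: "Assignment of patients will be made based on a sequential treatment assignment or minimization strategy". It then defines it: "each patient will be randomized to the treatment arm that would minimize differences between groups". On the factors it says "Randomization will be stratified by sex and surgery type", "so that the number of male/female patients and VRO/associated procedure patients will be balanced in each study group between trial arms". The task is central: "The Biostatistics Core of the HSS Healthcare Research Institute will randomize each patient based on the minimization strategy". No assignment probability, biased coin or tie rule appears in this section or elsewhere in the document.

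On blinding, the same section describes "all parties, except the pharmacy, anesthesiologist, and designated research assistant, being blinded to the randomization schedule". The Treatment Groups text adds that anesthesiologists know the arm of a patient.

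On recruitment, section 2 says "A research assistant will review the office and operative calendars of the study surgeons each week to identify and recruit potential patients", and on consent, "All authors on the protocol, in addition to their research assistants, will be designated to obtain consent". Consent is taken before surgery at the preadmission visit. The document does not say whether the assignment is made before or after consent, or whether the unblinded assistant is a different person from the one who recruits.

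**The concern.** Minimization without a random element is a calculation. Given the past assignments and the next patient's factor levels, the next arm is fixed unless the scores tie. Here there are only two factors, both binary, and both can usually be known before a patient is approached: sex, and whether the planned operation includes associated procedures. Central assignment conceals a list, but it cannot conceal a rule that someone else can recompute from known inputs.

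If a person who recruits or takes consent can foresee the arm, that knowledge can affect who is approached and when. The trial is small (24 patients required, 30 to be enrolled), so steering a few cases expected to bleed more could shift the comparison of mean blood loss. The planned regression adjusts for age, sex, BMI and anesthesia type. It omits surgery type and cannot capture unrecorded judgment about whom to approach.

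**Working it through.** The document gives no figure for predictability, so there is none to reproduce. The check asks how predictable the rule is if followed as written.

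**Inputs from the protocol.** 30 allocations, two arms of equal size, two binary factors (sex, surgery type), each patient sent to the arm that reduces imbalance.

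**Assumptions.** Ties are broken 50:50. The share of males is 0.5-0.6 and the share with associated procedures 0.5-0.9, since the document gives neither. Results hardly change over these ranges.

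**Balancing rule.** The text is open to more than one reading. Its reference to numbers of male/female and of VRO/associated-procedure patients points to marginal totals. The word stratified allows balance within the four sex-by-surgery cells. A third version also balances the overall arm totals.

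**Relation used.** Let f be the share of assignments where one arm is favored, and p the probability of assigning that arm. A person with the full tally guesses the favored arm, and guesses at random on ties:

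correct guesses = f × p + (1 − f) × 0.5

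With p = 1, f is also the share of assignments that are forced.

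**Results by Monte Carlo, 30 patients.**

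| Balance sought | Forced, p = 1 | Guessed with full tally, p = 1 | Guessed with full tally, p = 0.8 |
|---|---|---|---|
| Marginal totals | 70-71% (about 21 of 30) | 85-86% | 72-73% |
| Marginal plus overall total | 77-78% | 88-89% | 74-75% |
| Within four cells | about 47% (about 14 of 30) | 73% | 67% |

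Checks by hand:
- Marginal, p = 1: 0.70 × 1 + 0.30 × 0.5 = 0.85.
- Within-cell, p = 1: 0.467 × 1 + 0.533 × 0.5 = 0.73.
- Marginal, p = 0.8 (f rises to about 0.73): 0.73 × 0.8 + 0.27 × 0.5 = 0.72.

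**Incomplete knowledge.** The figures above require the complete tally. Under the marginal rule with p = 1 (assumed 55% male, 70% with associated procedures), if the guesser knows only a random share of past assignments:

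| Share known | Correct guesses |
|---|---|
| All | 85% |
| 90% | 72% |
| Half | 58% |
| One third | 56% |
| One quarter | 55% |
| None | 50% |

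Predictability falls quickly, because each missing assignment can reverse the apparent imbalance.

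**Price of the random element.** Under marginal balance, moving from p = 1 to p = 0.8 raises the mean difference in arm size from 0.3 to about 1 patient. The 95th percentile goes from 2 to between 2 and 4, depending on the assumed factor mix.

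**The case against.** The strongest reply is that the protocol is short and silence is not proof. It says patients will be randomized and gives the task to a biostatistics unit, which may well use a random element that the text does not mention. That stands: the document supports the statement that no random element is specified, and does not show that none is used. The two method labels joined by *or* are also settled in effect by the later sentence that names minimization.

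Safeguards exist. Surgeons, medical staff and patients are blinded to the schedule. All bilateral VRO patients of the study surgeons are to be screened, with reasons for ineligibility or exclusion recorded on the CONSORT diagram, which limits selective approach and makes it visible. Surgery is elective and scheduled, and a research assistant is not described as controlling dates. The recruiting assistant and the unblinded one may be different people. These points lower the risk. They do not remove it, because the overlap of roles is not ruled out and the timing of assignment relative to consent is not stated.

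A reader might infer that every anesthesiologist could predict about 85% of allocations, since they are all unblinded. The document does not support this. It says they know a patient's arm, not that each holds the tally for all patients, and it refers to several participating anesthesiologists. One who knew half of the past assignments would guess about 58%. The pharmacy may hold the full list but is given no part in recruitment.

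A reader might also infer that the t-test is invalid under this allocation. No type I error was calculated, and this point makes no such claim.

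**Conclusion.** The concern holds as one of exposure. Followed as written, the rule forces about 70% of assignments under marginal balance, the most natural reading, with a range of 47% to 78% across the plausible balancing rules. Someone with the complete tally would guess about 85% (73% to 89%), against 50% with no knowledge of past assignments. The statement that most allocations are forced therefore depends on the reading, since on the within-cell version slightly under half are.

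The result rests on three conditions: that the biostatistics unit applies the rule with no random element, that a person who recruits or takes consent holds essentially the full list, and the assumed factor prevalences, which matter little. The designated research assistant is the person most likely to meet the second condition, and the document does not exclude it. It would go too far to conclude that selection bias occurs or occurred; nothing in the document shows that. The change is worth making because a better method is available at very low cost.

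**What to change.** In the Randomization Process section, state one method: minimization on sex and surgery type with a random element, for example probability 0.8 for the balancing arm and 0.5 for ties, run by the Biostatistics Core. State whether balance is sought on the margins or within cells. Add that the assignment is released only after consent is logged, and that the unblinded research assistant does not recruit or obtain consent. If any of this is already practice, it need only be written down.

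With probability 0.8 no assignment is certain, and full-tally guesses fall to the levels in the last column of the first table. The role separation does the rest, since a recruiter who knows no past assignments guesses at 50%. The cost is one parameter in the allocation program, a few sentences of protocol text, and the slightly larger chance imbalance in arm size shown above.
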